- **Primary Outcome:** measuring the rate of anterior segment retraction for space closure when frictionless and friction mechanics were used.

Secondary Outcomes: measuring the changes in incisal position with regards to tip, torque and vertical position following

Outcome measure:

Outcome measure	Measure tool	Measure unit
1 ^{ry} Outcome	Assess the rate of anterior segment retraction	Digital scanned dental models. mm
2 ^{ry} Outcomes	1) Assess amount of anchorage loss.	Digital scanned dental models. mm
	2) Pain	Pain scoring sheets given to patients. VAS scoring from 1-10

B-Research question:

In orthodontic adolescent patients in need of 1st premolar extractions followed by anterior segment retraction, is there a difference, in terms of rate of anterior segment retraction, between friction and frictionless mechanics?

Objectives of the study

Research hypothesis:

The null hypothesis of this research is that there is no difference in rate of anterior segment retraction between friction and frictionless mechanics.

Primary objective:

Measuring the rate of anterior segment retraction using frictionless versus friction mechanics.

Secondary objectives:

Assess amount of anchorage loss and pain experienced.

Study design:

This is a randomized clinical trial with two arms parallel group and 1:1 allocation ratio. In one group, frictionless mechanics will be applied during anterior segment retraction while the other will receive friction mechanics during retraction to compare the results for differences in rate.

Materials and Methods

I)participants, interventions, and outcomes

A] Study Setting:

The study will be performed in the clinic of the Orthodontic Department at the Faculty of Oral and Dental Medicine, Future University. The recruited sample would be from the Egyptian urban and rural population.

B] Eligibility criteria:

- **Inclusion criteria:** for the participants include the following:
 1. Adolescent patients (females only).
 2. Patients requiring 1st premolars extraction followed by anterior segment retraction.
 3. Patients with fully erupted permanent teeth (not necessarily including the 3rd molar).
 4. Cases requiring maximum anchorage during anterior segment retraction.

- **Exclusion Criteria:** for the involved subjects included:
 1. Patients suffering from any systemic diseases interfering with tooth movement.
 2. Patients with extracted or missing permanent teeth. (except for third molars).
 3. Patients with badly decayed teeth.

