 4. Patients with any parafunctional habits.

C] Interventions:

➤ Medical History Questionnaire:

For every patient to exclude the presence of any systemic condition interfering with orthodontic treatment.

➤ Clinical Examination:

Oral structures will be examined to identify caries, fracture or missing teeth. Gingival tissues will be carefully examined for any gingivitis, periodontitis, recession or lesions.

➤ Diagnosis

Check the potential patient to fulfill the previously mentioned inclusion criteria. Every participant will be asked to sign an informed consent about the study. Full set of records (study models, lateral cephalometric radiographs, photos) will be taken for every patient as part of the routine procedure for treatment of patients in the clinic of the Orthodontic Department, Future University.

➤ Clinical Procedure:

After taking pre-treatment records, every patient will undergo:

- Bonding of all teeth except for first premolars, banding/bonding the first and second molars will be done using bidimensional brackets Roth prescription (0.022 slot prescription brackets)
- Levelling and alignment for the bonded and banded teeth will be initiated which will be done by following the wire sequence: 0.014 NiTi , 0.016×0.022 NiTi and 0.017×0.025 StSt.
- Then miniscrews will be placed in upper arch between 2nd premolar and 1st molar.
- The patient will be referred for extraction of 1st premolars then canine retraction will take place on a 0.017×0.025 StSt arch wire.

- Once canine retraction stage is completed, the patient will be referred for the taking of pre-intervention records.

➤ **Acquisition of pre-intervention records:**

- Impressions will be taken followed by digital scanning for the produced stone models which are the T_0 record.

➤ **Beginning of Retraction:**

Frictionless group:

- A ligature wire extending between the canines and mini-screws will be used for proper anchorage control.
- Closing retraction T-loops will be fabricated using 0.017 x 0.025 TMA wire. The loop will be positioned in half the remaining extraction space after canine retraction. [15], [16].
- A gable angle of 45° will be added.
- Distal activation of 4 mm will be done that will produce around 160 g per side of retraction force[17], with cinch back the wire distal to 2nd molars bilaterally.

Friction group:

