- Crimbable hooks added to the arch wire (0.017"x0.025" Stainless steel) distal to the lateral incisor passing through the center of resistance of the anterior segment.
- A ligature wire extending between the canines and mini-screws will be used for proper anchorage control.

- Retraction will start on a 0.017"x0.025" Stainless steel wire with an elastomeric power chain (force applied will be 160 g) extending between the crimpable hooks and the mini-screws.
- The force will be measured by a force gauge and reactivated each visit to maintain force of retraction constant all over the retraction phase.

➤ **Follow up visits**

Patients will be asked to attend for follow up sessions every 4 weeks for:

- Evaluation of the mini implants stability.
- Replacement of the power chain to maintain a force of 160g.
- Reactivation of the T-loop by further distal activation and cinch back.

➤ **Criteria for discontinuing or modifying the allocated intervention:**

In cases of prolonged swelling or pain related to the miniscrew the patient will be given strict oral hygiene measures and may wait for three weeks before the beginning of retraction.

In cases of loose or broken miniscrews, the screw will be removed and replace the miniscrew after total resolution of the inflammation.

➤ **Post-retraction Questionnaire:**

The patients of both groups will be asked to fill in questionnaires regarding their experience with both techniques.

➤ **Retraction records**

The scanned dental models will assess the rate of retraction and molar anchorage loss achieved throughout the study.

➤ **Material Used**

- American Orthodontics Brackets, Roth prescription, Bidimensional slot size.
- American Orthodontics Elastomeric power chains
- American Orthodontics Elastomeric O-ties
- American Orthodontics Ligature wire.
- Jeil, Mini Screws, 8 mm length.
- American Orthodontics Arch wires.
- American Orthodontics Molar bands/tubes.

D] Outcomes

[figure not shown]
Primary outcome: is to monitor the rate of anterior segment retraction using both frictionless and friction methods.

Secondary outcomes is to monitor anchorage loss and pain, in association with each technique after retraction during anterior segment retraction,. All outcomes will be assessed as the difference between T_0 at the start of anterior segment retraction after full canine retraction and T_{final} after complete space closure.

E] Participant timeline:

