1. The principle investigator will screen the potential patients through careful clinical examination of patients at the orthodontic department, Faculty of Oral and Dental Medicine, Future University.

2. All recruited patients should fulfil the previously mentioned inclusion and exclusion criteria.
3. Every participant will be asked to sign an informed consent before the beginning of the study.
4. After patient's enrolment, each participant will be asked for pre-intervention records to ensure proper diagnosis.
5. The supervisor will randomly allocate the patients to one of the intervention groups.
6. Active intervention will begin after proper leveling and alignment of the upper and lower arches and canine retraction.
7. The principle investigator will take pre-retraction records for every participant. (T_0)
8. In Friction mechanics group, Power chain is used for anterior segment retraction while in Frictionless group, T-loop is used for retraction.
9. Each patient will come every 4 weeks for follow up visit, for appliance activation and uptake of impression for interim records.
10. After complete space closure, the principle investigator will take post-retraction records for each participant. (T_{final})
11. Every patient will fill up a questionnaire regarding his experience during treatment.
12. The principle investigator will continue the normal treatment and achieve proper finishing for every patient after the end of the study.

CONSORT flow chart of the flow of participants in the study.

E] Sample size calculation:

Our sample size calculation is based on a previous study comparing the effect of friction and frictionless mechanics. [14]

F] Recruitment strategy:

The principal investigator will recruit the patients from the clinic of Orthodontic department, Faculty of Oral and Dental Medicine- Future University.

Screening of patients will continue until the total number of participants for the study is collected.

II) Assignment of interventions:

A] Sequence generation:

The supervisor of the study will apply Computer generated random numbers to randomly assign patients to Group A (Friction) or B (Frictionless) using Microsoft Office Excel 2007 sheet. and will write the patient numbers in the first column, and will select function RAND() to generate the randomization number in the second column. These numbers will be sorted according to the randomization number so the first column numbers will be randomly distributed.

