B] Allocation concealment mechanism:

The supervisor of the study will write the randomization numbers of the patients in opaque white papers folded three times to form sealed envelopes and store it inside a box. Then will keep the Codes for randomization at the secretary office.

C] Implementation:

At time of intervention, the main operator will send the patient to the secretary office. Then, the assigned employee will open the box and ask the patient to select one envelope. the main operator will assign each participant for the

corresponding intervention either (friction or frictionless group) according to the list of codes of randomization.

Assignment to either intervention will occur before leveling and alignment stage.

D] Blinding:

Blinding of the operators: Blinding will not be possible for the operators during the application interventions and during the follow up visits. The principal operator is responsible for assigning subjects to interventions according to the concealed allocation, appliance activation at follow up visits, dental impressions and acquisition of dental casts.

Blinding of the outcome assessors: It is a single blinded study, the outcome assessors only will be blind. The patients name will be sealed from pre and post study models. Then two assessors will carry on, blindly and independently, the measurements and analysis of the study.

III) Data collection, management and analysis:

A] Data collection methods:

Primary outcome:

1. Retraction rate: to assess the antero-posterior movement of anterior teeth and first molars, the principle investigator will take study models for every participant monthly during the follow up visits. Then will digitize the models and identify the landmarks, reference lines and planes on the pre, interim and post-retraction digital dental models for measurements reading.

Secondary outcomes:

- 1. Anchorage loss:*** will be accessed by the principal investigator via scanned study models before and after the completion of retraction by identifying the landmarks, reference lines and planes, then will interpret the measurements in degrees and millimeters.
- 2. Pain:*** Each patient will fill a questionnaire regarding his treatment experience in a VAS scoring from 1-10. The questionnaire will include several questions related to oral hygiene, pain and discomfort experienced throughout the trial.

B] Data management:

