A colleague outside the research team will enter the data and organize it in excel sheets in the computer of the orthodontic department.

Data will include all photographs, models, radiographs and filled questionnaire.

C] Statistical Analysis:

- The principle investigator will be responsible for the extraction of the required data from the study models taken at every follow up visit. The data will be sent to a specialized statistician.
- The specialized statistician will be responsible for the statistical analysis of the study by:
 1. Presenting the data as mean, standard deviation (SD) and Standard error (SE) values.
 2. Using Paired t-test to compare between the friction and the frictionless group of retraction as well as to compare between the pre-and post -treatment data for each group.
 3. Using Kolmogorov Smirnov and Shapiro Wilk tests to determine the rate of anterior segment retraction.

4. Statistically evaluate the patient acceptance for both techniques.

- For this study, the specialized statistician will use IBM11 SPSS12 Statistics Version 20 for Windows to perform the required statistics.
- The significance level will be $P \leq 0.05$. Highly significant variables are detected when P value is less than 0.01.

Assessors Reliability:

- To achieve high reliability for measurements, the supervisor will choose a well-experienced inter-examiner during the study.
- A training session will be provided for the examiners to ensure standard measurements techniques.
- Each examiner will complete the measurements on a model and will repeat the procedure after one week to assess the intra- and inter-examiner reliability.
- The supervisor will compare the measurements of the two assessors for disagreement with a difference of more than one millimeter.
- The supervisor will evaluate the amount of variation in measurements among and between examiners to test the performance of each assessor.
- The examiner with less reliability will receive additional training but will be replaced during the study.
- The specialized statistician will calibrate the intra and inter-examiner reliability for the measurements of the study by Inter-observer and intra-observer reliability was assessed using $P \leq 0.05$.

IV) Method Monitoring:

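### The between-arm comparison ignores the residual extraction space on each T_0 scan, which nearly fixes the retraction distance as the outcome is written; the cost is precision and robustness, not bias

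*Combined protocol and SAP*

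**What the plan says.** **Design.** The Study design section states: "This is a randomized clinical trial with two arms parallel group and 1:1 allocation ratio". Section II A] allocates by an unstratified spreadsheet sort; the supervisor "will select function RAND() to generate the randomization number in the second column". No balancing factor is named.

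**Between-arm analysis.** The only test named for the arms is in section III C], item 2: "Using Paired t-test to compare between the friction and the frictionless group of retraction". No covariate appears there or elsewhere.

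**The starting record.** Section I C], on pre-intervention records, applies once canine retraction is finished: "Impressions will be taken followed by digital scanning for the produced stone models which are the T_0 record". The space still to be closed can be read from that scan, although the plan names no such measurement.

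**The outcome.** Section I D] says: "All outcomes will be assessed as the difference between T_0 at the start of anterior segment retraction", with the end point at complete closure. The outcome table gives mm as the unit for both the primary outcome and anchorage loss. The primary outcome is nevertheless called a rate throughout, and section III A] has models taken monthly.

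**Timing.** Section II C] says: "Assignment to either intervention will occur before leveling and alignment stage". T_0 therefore comes after allocation. Section II D] says the operators are not blinded and the outcome assessors are.

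**Size.** The sample size section offers only this: "Our sample size calculation is based on a previous study comparing the effect of friction and frictionless mechanics". It gives no N, SD, effect or power.

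**The concern.** Follow-up ends when the space is closed. At that point, incisor retraction plus forward movement of the posterior teeth roughly equals the space present at T_0. Patients start with different spaces, so an outcome in mm from T_0 to closure carries that variation almost whole into the error term. Correcting the paired test to an unpaired one would leave it there.

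Two things are at stake. Standard errors for the mm outcomes are larger than they need be. And in a small trial with unstratified allocation, the realised estimate can sit some way from the truth because one arm happened to draw larger spaces. Both can be reduced with a distance read from scans the trial already takes.

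**Working it through.** The plan has no figure of its own to reproduce, since N, SD and effect are all absent. What follows illustrates size under stated assumptions.

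**Notation.** S is T_0 space, A is anchorage loss, D = S − A is retraction distance at closure, n is patients per arm, and r is the within-arm correlation of S with the outcome.

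**Assumed inputs.** S has mean 5 mm and SD 0.5 to 1.5 mm. A has mean 0.3 mm and SD 0.2 mm; the plan's literature review cites 0.2 to 0.88 mm with mini-screws. The closure rate is 0.9 mm/month with SD 0.4, independent of S; the review cites 0.87 to 0.91 mm/month with SDs 0.34 to 0.46, for canines. Closure is recorded at monthly visits.

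**1. Retraction distance in mm.** If A is independent of S, r = SD(S)/√(SD(S)² + SD(A)²).
- SD(S) = 0.5: 0.5/√(0.25 + 0.04) = 0.93
- SD(S) = 1.0: 1/√(1 + 0.04) = 0.98
- SD(S) = 1.5: 1.5/√(2.25 + 0.04) = 0.99

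Simulation with A held at or above zero gives 0.94 to 0.99.

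**2. Anchorage loss in mm.** Suppose A = kS, with k of mean 0.3/5 = 0.06 and SD 0.2/5 = 0.04. Then r = 0.06·SD(S)/√[0.06²·SD(S)² + 0.04²·(25 + SD(S)²)], which is 0.15, 0.28 and 0.40 for SD(S) = 0.5, 1.0 and 1.5. Simulation with k held at or above zero gives 0.16 to 0.42. If A does not depend on S, r is 0. The documents do not say which applies.

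**3. Rate in mm per month.** Simulating D divided by months to closure gives r of about 0.03 to 0.14, depending on the assumptions. It rises to about 0.28 if a start-up lag is added.

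**4. What adjustment is worth.** Variance of the adjusted difference relative to the unadjusted one is (1 − r²)(1 + 1/(2n − 4)); the second term is the cost of estimating the slope. The equivalent gain in patients is the reciprocal.

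| r | n = 10: variance factor (gain) | n = 15: variance factor (gain) |
|---|---|---|
| 0 | 1.06 (0.94) | 1.04 (0.96) |
| 0.1 | 1.05 (0.95) | 1.03 (0.97) |
| 0.3 | 0.97 (1.03) | 0.95 (1.06) |
| 0.5 | 0.80 (1.25) | 0.78 (1.28) |
| 0.94 | 0.12 (8.1) | 0.12 (8.3) |

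Break-even is |r| = √(1/(2n − 3)), which is 0.24 at n = 10 and 0.19 at n = 15. Distance in mm is far above it. Anchorage loss may fall on either side. A rate is mostly below it, and above it only under the lag assumption.

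**5. Chance imbalance.** The standardised difference in S between arms has SD √(2/n). The chance that it exceeds 0.5 SD in either direction is 26%, 22% and 17% at n = 10, 12 and 15. Such an imbalance moves the unadjusted estimate by at least 0.5r outcome SDs: 0.47 at r = 0.94, 0.25 at r = 0.5, and 0.05 at r = 0.1.

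**The case against.** **The primary outcome is a rate.** Space sets how far there is to go and so how long closure takes; it does not set mm per month. This stands. A reader might infer that T_0 space determines the primary outcome and that precision on it is certainly lost. The documents give no correlation for a rate, and plausible values mostly lie below break-even.

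**In mm, adjustment changes the question.** Given S, the arm contrast in D is the anchorage-loss contrast with its sign reversed. That is true, but it holds equally for the unadjusted contrast: preparation up to T_0 is the same in both arms, so S has the same expectation in each and both contrasts estimate the same quantity. Adjustment only removes noise. What stands is that neither mm contrast measures speed, so adjustment cannot replace a proper definition of the rate.

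**Randomisation already deals with imbalance.** It does on average, and a correct independent-groups standard error allows for it. A reader might infer that the unadjusted comparison is biased; it is not.

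**T_0 space is measured after allocation.** This stands as a caution. The described preparation does not differ by arm, so space should not be an effect of the mechanics compared. But the operator is unblinded, a difference in T_0 space need not be pure chance, and adjustment may not remove whatever else came with it.

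**The paired test is the more basic fault.** Agreed; it suits neither the design nor unequal arms. It is a separate fault, since an unpaired t-test would also ignore space.

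**Conclusion.** The point holds for the outcomes as written, meaning mm from T_0 to closure. There T_0 space almost determines retraction distance (r about 0.94 to 0.99) and may be related to anchorage loss (about 0.16 to 0.42 if loss is proportional to space). Leaving it out loses precision and robustness.

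For a rate in mm per month, the documents support no more than a pre-specified sensitivity analysis. A compulsory space-adjusted primary analysis of the rate does not follow from them.

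All sizes rest on assumed r, n, space and anchorage-loss distributions, because the plan gives neither r nor N. The weight is moderate: a cheap improvement that should be made, ranking below defining the rate and replacing the paired test.

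**What to change.** 1. Replace the paired between-arm test in item 2 with an independent-groups linear model.
2. For retraction in mm and for anchorage loss, pre-specify T_0 residual space as a covariate: the mean of right and left, read from the existing T_0 scans by the blinded assessors.
3. Define the primary rate per unit time, for example mm per month from the monthly models, and reconcile this with the mm unit in the outcome table and the T_0-to-closure definition in I D]. Take the unadjusted independent-groups comparison as primary for the rate and the space-adjusted model as a pre-specified sensitivity analysis.
4. Report T_0 space by arm, and state that it is measured after allocation and why adjusting for it is considered acceptable.
5. Give adjusted and unadjusted differences, each with a 95% CI.

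**Cost.** A few sentences in the analysis section, one distance per side from scans already taken, and one degree of freedom. If space proves not to be prognostic (r between 0 and 0.1), the adjusted variance is about 3 to 6% larger at 10 to 15 per arm.

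### The pre/post tests within each arm do not address the between-arm question; conclusions, including those on anchorage loss, should rest on the between-arm difference with its 95% CI

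*Combined protocol and SAP*

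**What the plan says.** The trial is described under Study design as having "two arms parallel group and 1:1 allocation ratio". The null hypothesis, under Objectives of the study, is that "there is no difference in rate of anterior segment retraction between friction and frictionless mechanics". Both are statements about a difference between arms.

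Section III) C] Statistical Analysis, item 2, gives one test two jobs. The first is between arms: "Using Paired t-test to compare between the friction and the frictionless group of retraction". The second is within arms: "as well as to compare between the pre-and post -treatment data for each group". Item 1 lists the summary output: "Presenting the data as mean, standard deviation (SD) and Standard error (SE) values". The section then sets a 5% significance level and a second tier: "Highly significant variables are detected when P value is less than 0.01". No between-arm difference with a confidence interval is listed. Nothing says which P value decides, or that the within-arm tests are descriptive.

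On timing, the Participant timeline (item 10) states: "After complete space closure, the principle investigator will take post-retraction records for each participant". Section D] Outcomes defines all outcomes as the difference between T0, the start of anterior segment retraction, and Tfinal, after closure. Anchorage loss is among them, measured on scanned models before and after retraction (section III) A]).

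**The concern.** A within-arm test asks whether teeth moved from T0 to Tfinal under one technique. The trial asks whether the two techniques differ. Two problems follow.

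- **Anterior tooth position.** Tfinal is reached only when the space is closed, so a null of no movement is false by design. The result carries no information about the mechanics.
- **Anchorage loss.** The between-arm clause of item 2 refers to the groups of retraction and does not mention anchorage loss, whereas the pre/post clause is general. A reader could be left with two separate P values, one per arm. If one is below 0.05 and the other is not, it is natural to conclude that one technique loses anchorage and the other does not. That is not a test of a difference, and it can easily happen when the arms are identical.

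**Working it through.** The documents give no sample size, SD, effect size or power, so there is no planned figure to reproduce. Everything below rests on stated assumptions, with a two-sided 5% level.

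**Step 1. Formula.** Let p be the power of a paired t-test within one arm, from the noncentral t distribution with n − 1 degrees of freedom and noncentrality (mean change / SD) × √n. If both arms have the same true change and are independent, the probability that exactly one arm is significant is 2p(1 − p). It peaks at 50% when p = 0.5. It is 32% at p = 0.2 or 0.8, 9.5% at p = 0.05 or 0.95, and 2% at p = 0.99.

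**Step 2. Anchorage loss, standardised change.** Assumed n is 10-15 per arm. Entries are within-arm power p, then 2p(1 − p).

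| n per arm | 0.3 SD | 0.5 SD | 0.7 SD | 1.0 SD | 1.5 SD |
|---|---|---|---|---|---|
| 10 | 0.136; 24% | 0.293; 41% | 0.506; 50% | 0.803; 32% | 0.987; 2.5% |
| 12 | 0.158; 27% | 0.353; 46% | 0.599; 48% | 0.883; 21% | 0.997; 0.6% |
| 15 | 0.192; 31% | 0.438; 49% | 0.713; 41% | 0.949; 10% | >0.999; 0.1% |

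Worked cell: n = 12 and 0.5 SD gives 2 × 0.353 × 0.647 = 0.457, or 46%.

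**Step 3. Anchorage loss in millimetres.** The literature review (Anchorage Requirements and Efficiency of Miniscrews) cites a study with 0.2 mm loss under mini-screws and gives no SD. Taking 0.2 mm as the true loss in both arms, the chance of significance in one arm only is:

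| Assumed SD | n = 10 | n = 15 | n = 20 | n = 30 |
|---|---|---|---|---|
| 0.2 mm | 32% | 10% | 2% | 0.1% |
| 0.3 mm | 50% | 44% | 31% | 11% |
| 0.5 mm | 33% | 42% | 48% | 49% |
| 1.0 mm | 16% | 20% | 24% | 30% |

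If the loss is large against its SD (0.5 mm with SD 0.3 mm, n of 10 or more), it is below 1%.

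**Step 4. Between-arm comparator.** In 200,000 simulated trials per setting (0.2 mm in both arms, SD 0.2-0.5 mm, n of 10, 15 and 20), an independent-samples t-test on the changes was falsely significant in 4.9-5.0%. In the same settings, significance in one arm only occurred in 2-50%.

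**Step 5. Anterior position.** The chance that the within-arm test gives P ≤ 0.05 at n = 10, with assumed mean movement and SD:

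- 4 mm, SD 2 mm: above 99.9%
- 3 mm, SD 1.5 mm: above 99.9%
- 3 mm, SD 2 mm: 98.7%
- 2 mm, SD 1.5 mm: 96%
- 2 mm, SD 2 mm: 80%, rising to 95% at n = 15

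The test is therefore near-certain to be significant when the mean movement is at least about 1.5 SD. Spaces closed to completion make that plausible.

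**The case against.** The strongest reply is that item 2 plans the friction-versus-frictionless comparison first and the within-arm tests only in addition, while the research question and null hypothesis are plainly between-arm. That stands. A reader might infer from the pre/post clause that the techniques will be judged by which arm reaches significance. The documents contain no such rule, so the percentages above are the error rate of a misreading and not of the planned analysis.

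A reader might also infer that the primary analysis is compromised. It is not compromised by this clause: the primary outcome is a rate, and a rate has no pre value to test against. The near-certain result concerns tooth position.

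Third, a reader might take 24-50% as a property of this trial. It is not. The range of 0.3-0.7 SD lies around the peak of 2p(1 − p), and outside it the figure can fall below 1%.

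Finally, whether molars moved at all under mini-screw anchorage is a fair descriptive question, and the literature review discusses it at length. Within-arm change should be kept, as an estimate. The P < 0.01 label is reporting style and is not part of this point.

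What remains after these objections is that the plan does not say which comparison decides, names no clear between-arm test for anchorage loss, and lists no between-arm estimate with an interval.

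**Conclusion.** The point holds in limited form. The within-arm tests are planned, do not bear on the trial's question, and are close to uninformative for anterior position. For anchorage loss, equal arms would show significance in one arm only in about 24-50% of trials if n is 10-15 per arm and the true change is 0.3-0.7 SD. The figure runs from below 1% to 50% over wider assumptions, and the documents supply neither n nor SD to narrow it. The consequence is a risk of misinterpretation, greatest for anchorage loss, and not an error built into a decision rule. This is a free improvement.

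**What to change.** Amend item 2 of the Statistical Analysis section in three respects.

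- For retraction rate, and for anchorage loss as the T0-to-Tfinal change, state that the between-arm difference with its 95% CI is the sole basis for conclusions about the techniques.
- Name an independent-samples method for that difference, such as a two-sample t-test with its interval. The wording now applies a paired t-test to the arms, but they hold different patients and no pairs are defined. That is a separate and more serious defect in the same sentence, and this fix does not work unless it is corrected.
- Report each arm's mean change with its 95% CI as description only, without a hypothesis test.

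The cost is SAP wording. No additional data, patients, visits or procedures are needed.

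### Pain is a declared secondary outcome, but its instrument and time point are inconsistent, and the statistical section names an analysis of patient acceptance instead of pain

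*Combined protocol and SAP*

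**What the plan says.** All places are in the combined protocol and SAP.

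- **Objectives of the study, Secondary objectives:** "Assess amount of anchorage loss and pain experienced".
- **Outcome measure table:** the tool and unit for pain are "Pain scoring sheets given to patients. VAS scoring from 1-10".
- **I) D] Outcomes:** pain is again a secondary outcome, with no scale named. The section then sets a general rule: "All outcomes will be assessed as the difference between T_0 at the start of anterior segment retraction after full canine retraction", with T_final, after complete space closure, as the other end point.
- **III) A] Data collection methods, Secondary outcomes, item 2 (Pain):** "Each patient will fill a questionnaire regarding his treatment experience in a VAS scoring from 1-10". On content: "The questionnaire will include several questions related to oral hygiene, pain and discomfort experienced throughout the trial".
- **I) C] Interventions, Post-retraction Questionnaire:** "The patients of both groups will be asked to fill in questionnaires regarding their experience with both techniques". The Participant timeline (item 11) and IV) C] Harm likewise place the questionnaire at the end of retraction.
- **III) C] Statistical Analysis, item 4:** "Statistically evaluate the patient acceptance for both techniques". No variable, time point or test is attached.

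**The concern.** A secondary outcome needs the same content in the objective, the instrument, the time point and the analysis. Here they do not line up. The objective is pain. The data collection text describes a broader questionnaire. The timing rule asks for a change that the described data cannot give. The one patient-reported analysis concerns a different construct.

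At stake is whether the trial can give a prespecified answer on pain. As written, the statistician must choose after data collection which item or score represents pain, at which time, and with which test. Patients are not blinded (II) D] Blinding limits blinding to the outcome assessors), so a self-reported outcome is already open to expectation effects. Leaving the endpoint open adds room for selective reporting.

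**Working it through.** No arithmetic applies. The plan states no figure for pain: no sample size, SD, expected difference or number of questionnaire items. The check sets the sections side by side.

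**1. Construct.** Pain is named in the secondary objective, the outcome table, the Outcomes section and the heading of the data collection item. Acceptance appears in none of them. It enters only in item 4 of the Statistical Analysis, without an instrument.

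**2. Instrument.** The outcome table points to dedicated pain scoring sheets. The data collection section points to a questionnaire on treatment experience with at least three kinds of content: oral hygiene, pain and discomfort. Both use a 1-10 VAS. Nothing says whether the sheets and the questionnaire are the same document, how many pain questions there are, or which response is the endpoint.

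**3. Time point.** The general rule needs two pain scores per patient, one at T_0 and one at T_final. Three sections place the questionnaire after retraction. None describes a pain score at T_0, whether by questionnaire or by sheet. One score per patient cannot give a difference, so pain cannot be computed as the Outcomes section defines it. The questions also cover pain over the whole trial, so the score is a summary of the period and not a state at T_final.

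**4. Analysis.** The four items of the Statistical Analysis, tested against pain:

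| Item | Content | Does it specify a pain analysis? |
|---|---|---|
| 1 | Means, SD, SE | Descriptive only; no outcome named |
| 2 | Paired t-test between groups and pre/post | No outcome named; a paired test does not fit two independent arms; no pre-retraction pain score is described |
| 3 | Kolmogorov-Smirnov and Shapiro-Wilk tests | Tied to the rate of retraction |
| 4 | Patient acceptance | Different, undeclared construct; no test named |

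None of the four names pain. On the most generous reading, item 2 covers it, but its between-group test assumes paired observations that a 1:1 parallel design does not provide.

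**The case against.** The strongest reply is that this is loose drafting and the pain data will still exist. The outcome table names pain sheets, the questionnaire contains pain questions on a VAS, and the filled questionnaires are listed among the data to be managed. Items 1 and 2 are not limited to particular outcomes, so pain could be analysed there, with acceptance as an extra. This stands in part: pain data would probably be collected, and the plan does not exclude analysing them. It does not supply the endpoint, the time point or a suitable test.

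Three stronger readings are tempting, and the documents support none of them.

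- **That pain will be analysed as acceptance.** Item 4 does not say so. Its reference to both techniques echoes the wording of the Post-retraction Questionnaire, which makes a link plausible, but it remains an inference.
- **That oral hygiene items will be averaged with pain and dilute a pain difference.** No section mentions a total, mean or composite score; item-by-item analysis fits the text equally well. Any power figure would need an assumed sample size, item count and inter-item correlation. Depending on how many items differ between arms, averaging could lower or raise power.
- **That patients are asked to rate a technique they did not receive.** The phrase "fill in questionnaires regarding their experience with both techniques" is awkward in a parallel trial, but it can be read as each group reporting on its own technique, and the Participant timeline asks only about the patient's own treatment. This is a minor wording point.

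**Conclusion.** The concern holds in this form: the pain outcome has an unreconciled instrument and a change-score definition that the described data cannot meet, and the statistical section does not name pain but names an undeclared construct. The stated analysis therefore does not address the pain objective.

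The size is one of the two declared secondary outcomes. The primary outcome and anchorage loss are not touched by this point. No numerical loss is claimed. The conclusion rests on the text alone, and on one reading: that a T_0 pain score not described anywhere is not planned. If one is planned, the timing conflict disappears once it is written down; the instrument and analysis gaps remain. The change should be made, since it costs little and without it a reported pain result would not be prespecified.

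**What to change.** 1. **Outcome measure table and III) A] item 2:** state whether the pain scoring sheets and the questionnaire are one instrument. Define the outcome as the pain VAS item or items only, kept separate from the oral hygiene items, and give the time point. If there are several pain items, name the one used or the rule for combining them.
2. **I) D] Outcomes:** either exempt pain from the T_0 to T_final definition, or record the pain VAS at T_0 as well.
3. **III) C] item 4:** replace the acceptance analysis with a comparison of the pain VAS between arms by an independent-groups method, either a two-sample t-test or a Mann-Whitney test, chosen in advance. A paired test should not be used for this comparison.
4. **Other questionnaire items:** report them separately and descriptively. Either declare acceptance as an outcome with its own measure, or delete it.
5. **Post-retraction Questionnaire:** preferably refer to the technique the patient received.

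The cost is a wording amendment, plus one extra VAS per patient if a T_0 score is chosen. The small downside is that, if acceptance is deleted, it is no longer a tested result.
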